228 caregivers. We assume an exponential survival distribution with a median of 2 years and independent 2-year 10% attrition. Under these assumptions, we estimate the minimum detectable difference (MDD) between the intervention and control patient means at every 8 weeks post randomization for 48 weeks as described in Table 4. We apply this same method to caregivers (Table 5) who will have their follow-ups truncated at patient death. We use ENABLE II data to provide estimates for the caregiver MBCB-OB standard deviation (sd).¹²⁹ Based on the meta-analysis by Garin et al.¹⁹² Literature-based estimates are used for the KCCQ,¹⁹³ HADS,^{179,194} MSAS-HF,²⁵ and QOL-C.¹⁰⁴ Patient and caregiver MDDs shown in Table 4 and 5 are based on partially-conditional (on being alive) time-averaged tests of mean differences comparing the treatment groups at the specified follow-up times, intra-subject correlation of 0.5, with a corrected two-sided .01 significance level, and a power of 0.80. Under these conservative assumptions we have sufficient sample size for the primary aims of this study. For subgroup analyses (e.g. Caucasian race vs. other) the detectable time-averaged standardized difference in intervention effect by 48 weeks post randomization is 0.53, assuming equally sized subgroups, and prior to other covariate adjustment.

It is estimated that 120 patients (60 per group) will die by 48 weeks post-randomization and will be available for the analysis of patient outcomes nearest death. Based on the sds in Table 4, we find MDDs of 10.8 for KCCQ, 1.04 for MSAS-HF, 2.06 for HADS-A, and 2.01 for HADS-D. We project that the grief index (ICG) will be available for 37 caregivers in each group. With a sd of 11.7,⁶³ a 5% two-sided significance level and 80% power, the MDD of the ICG between two groups is 7.7 using a two-sample t-test.

For secondary comparison of survival outcomes, we make the same assumptions about median survival, attrition, accrual, and observation time as for the longitudinal outcomes. Based on a log rank test, .05 significance level and a power of .80, a 1-yr reference survival fraction of 0.68, the detectable HR is 1.6.

C6 Potential problems, alternative strategies, and benchmarks for success and future directions.

We have anticipated potential problems and solutions related to sample recruitment and retention, usual care group contamination, feasibility, non-participation and respondent bias. Recruitment and retention is expected to be robust based on the strong collaborative relationships between the HF and palliative care clinical and research teams and the availability of a large existing HF cohort. Research coordinators will be present in all HF clinical areas. The PI and co-PIs will meet regularly to track recruitment and review issues and jointly problem solve. While usual care group contamination is possible because HF clinicians are seeing intervention and usual care participants; early palliative care referral of HF patients at the UAB/BVAMC a very new concept^{22,39} as evidenced by the current negligible HF patients being seen in consultation. Our intervention is not specifically directed at changing physician behavior. Prior studies have shown that simply exposing physicians to new practices and providing education are not sufficient to change physician behavior⁶⁹ so while control group contamination due to physician behavior change is possible, it is extremely unlikely.²³ Feasibility is most directly addressed based on our prior successful completion of similar studies. Our team collectively has conducted numerous large, complex, multi-site RCTs in a rigorous fashion over the past decade. UAB/BVAMC is a research intensive environment (See Facilities/Resources) providing an exceptional infrastructure within which to conduct this study successfully. Non-participation bias will be monitored by collecting demographic data on person’s who decline and comparing that to patients who participate. We have established tracking and data collection mechanisms to capture this data carefully. Respondent bias in a non-blinded study is an important concern that we will address by providing similar information about the study purpose generally to both arms but not the specific outcomes we wish to influence and also by blinding data collectors to study group.

C7 Study Timeline and Milestones

As a result of our 10 years of experience conducting similar palliative care clinical trials our established investigators recruitment, retention, and data collection methods, we anticipate prompt regulatory approval (within 3 months of funding) and study start-up. This will ensure a 42-month recruitment period and an additional 6 months of follow up on patient and caregiver (bereavement) outcomes. We will present yearly progress reports to the Data Safety Monitoring Committee for feedback on study progress and to identify solutions to any unforeseen challenges or adverse events.

Activity	Year 1				Year 2				Year 3				Year 4				Year 5			
	Q 1	Q2	Q3	Q4	Q 1	Q2	Q3	Q4	Q 1	Q2	Q3	Q4	Q 1	Q2	Q3	Q4	Q 1	Q2	Q3	Q4
Aim 1 & 2																				
Hire, train staff, IRB approval																				
Enrollment																				
Collect Data																				
Data Analysis (exploratory aims (1&2))																				
Progress/Final Reports																				
Grant submission																				

REFERENCES

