Participant receipt / enactment of intervention: Following the collection of outcome measures at week 48, all intervention participants will be interviewed by phone for the primary purpose of determining if the patient received and enacted the components of the intervention as described in Table 2. We will use procedures and interview guides that have been adapted from our previous RCTs.⁶⁷ Briefly we will digitally-record, transcribe all interviews verbatim, and code transcripts using ATLAS.ti software to determine the extent of patient receipt and enactment of the skills taught by the nurse coaches. The PI is an experienced qualitative researcher,¹⁷⁰⁻¹⁷⁴ with expertise in the qualitative techniques that are recommended for intervention evaluation.^{175,176} Though not the purpose in this proposal, these interviews may also provide rich data for a secondary analysis of the patient and caregiver experience.

C4 INSTRUMENTS (All instruments are contained in Appendix E.)

The instruments were carefully chosen to measure distinct constructs within the theoretical models (Figures 1a and 1b) with little to no overlap. The proposed instrument battery and schedule are similar to what we have used in our prior studies^{50,51,177} and in our recent HF pilot study.⁶⁸ Per pilot participants' report⁶⁸ these presented minimal burden.

Table 3. Outcome measures

Specific Aim 1					
	Construct	Instrument	Description	Reliability	Schedule
HF Patients	QOL	Kansas City Cardiomyopathy Questionnaire (KCCQ) ¹⁷⁸	5 domains: physical limitations, symptoms, self-efficacy, social interference, and QOL; 23 items	Subscales α =.62 to .90	Baseline, week 8 and every 8 weeks until week 48
	Mood	Hospital Anxiety and Depression Scale (HADS) ¹⁷⁹	2 domains measuring depression and anxiety; 14 items	Subscales α =.82 to .83	
	Symptom Burden	Memorial Symptom Assessment Scale-HF (MSAS-HF) ²⁵	Targets 32 HF-relevant symptoms (e.g. chest pain, difficulty breathing while lying flat, etc.)	Subscales α =.73 to .92	
	Resource use	Resource Use	Inpatient days, ICU days, ED visits, hospice use, palliative care provider visits, AD completion, DNR orders	NA	
Specific Aim 2					
Caregivers*	QOL	Quality of Life – Caregiver (QOLC) ¹⁸⁰	3 domains: emotional and spiritual well-being; relationship with patient; & sleep, daily routine, and family life, 35 items	α = 0.91	Baseline, week 8 and every 8 weeks until week 48
	Mood	Hospital Anxiety and Depression Scale (HADS)	Same as above	Same as above	

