	Caregiver burden	Montgomery Borgatta Caregiver Burden Scale (MBCB) ¹⁸¹	Measure of caregiver burden with 3 domains: objective burden, stress burden, and demand burden; 14 items	Subscales α = .75 to .88	
	Self-reported health	PROMIS SF Global Health ¹⁰	2 domains: physical and mental health, 10 items	Subscales α = .81 to .86	
Exploratory Aims					
HF Patients	Patient Activation	Patient Assessment of Chronic Illness Care (PACIC) ¹⁸²	5 dimensions: activation, delivery system/decision support, goal setting, problem solving, and coordination; 20 items	Subscales α =.62 to .90	Baseline, week 8 and every 8 weeks until week 48
	Coping style	Brief Cope	2 subscales: active and avoidant coping; 28 items ¹⁸³	α = .68 to .79	
	Social support	Multidimensional Scale of Perceived Social Support (MSPSS)	Perceived adequacy of support from family and friends, 12 items ¹⁸⁴	α =.81	
All	Health literacy	Newest Vital Sign ⁹	Measure of health literacy and numeracy based on interpretations of a nutrition label, 6 items	α = .76	Baseline only
	Demographics	Demographic questionnaire	Age, gender, race, marital status, religion, employment, education, occupation, health insurance, smoking, etc.	NA	

Additional measures and data

If patients die on study we will conduct a standardized interview with a study or non-study (if agreeable) caregiver 2 months after death using the instruments and similar techniques from prior studies^{129,185} to evaluate the caregivers' perception of the EOL care provided and to assess their grief experience and mood. The questionnaires are: 1) proxy-reported Quality of Death and Dying (QODD) (31-items) which rates the quality of the descendant's last 7 days; it has acceptable internal consistency (Cronbach alphas 0.89) and construct validity;^{186,187} 2) Inventory of Complicated Grief-Short form (ICG-SF) a reliable, validated 13-item survey of complicated grief¹⁸⁸ and the HADS (described above).

C4.1 Data Collection, Management, and Quality Control.

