determining the profile characteristics (e.g. race, SES, gender, military vs. civilian background, absence of caregiver, etc.) of the participants who benefited the most and the least from the intervention using flexible modeling techniques, such as latent class analysis and recursive partitioning.

Specific Aim 2 Caregiver QOL, mood, self-reported health, burden

Caregiver outcomes will be analyzed using the same longitudinal methods as outlined for Specific Aim 1. For the analyses going forward in time from baseline, the effects of patient death on caregiver outcomes will be examined using models with indicators for patient death at its respective time-point. Only decedents' caregivers will have grief outcomes analyzed which will not involve longitudinal modeling. Caregivers of patients who die will contribute the additional outcome of a rating of quality of care at the end of life (QODD). Since only one QODD observation will be available for each decedent, no longitudinal modeling is required. However, analysis of these measures will be conducted with mixed effect methods to account for nesting, with the parameter of interest being the association between group assignment and the caregiver-rated outcome

Exploratory Aim 1. Explore mediators/moderators of patient/caregiver outcomes and reciprocal relationships.

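### No baseline covariate is pre-specified for the caregiver grief score (ICG-SF) or the post-death HADS, although enrolled caregivers already have a baseline HADS

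*Combined protocol and SAP*

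**What the plan says.** Section C4, under the additional measures, plans an interview with a study or non-study caregiver two months after a patient's death. Its purposes are to obtain the caregiver's view of end-of-life care "and to assess their grief experience and mood". The instruments are the QODD, the ICG-SF and the HADS.

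Table 3 schedules the HADS and the burden scale for enrolled caregivers at "Baseline, week 8 and every 8 weeks until week 48". Post-death HADS therefore has its own baseline, and ICG-SF has a baseline measure of distress from the same person.

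On analysis, C5.2 (Specific Aim 2) says that only decedents' caregivers "will have grief outcomes analyzed which will not involve longitudinal modeling". After a sentence on the QODD it adds that the measures will be analysed by mixed-effect methods to allow for nesting, "with the parameter of interest being the association between group assignment and the caregiver-rated outcome". No baseline covariate is named.

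On size, C5.3 states: "We project that the grief index (ICG) will be available for 37 caregivers in each group". "With a sd of 11.7", "a 5% two-sided significance level and 80% power", it concludes that "the MDD of the ICG between two groups is 7.7 using a two-sample t-test".

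A general rule in C5.2, under Specific Aim 1, provides for adjustment for baseline factors that turn out imbalanced or that predict compliance or missing data not due to death.

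**The concern.** The ICG comparison has the smallest groups for which the plan states a detectable difference, so precision matters most here. A caregiver's distress at enrolment plausibly predicts both grief and mood after bereavement. If it is left out of the model, the variation it explains stays in the error term.

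Because grief is excluded from the longitudinal models, baseline does not enter through a repeated-measures structure either. If the covariate is not named beforehand, whether to adjust and for what is decided after the data are seen.

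The comparison is also confined to caregivers of patients who died. That subset is formed after randomisation, so randomisation does not guarantee that the two groups had similar distress at entry.

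**Working it through.** **Inputs**
- From C5.3: 37 caregivers per group, SD 11.7, two-sided 5%, power 80%.
- From C5.3: 60 deaths per group by week 48, taken as stated. From C2.3: about 60% of patients have a participating caregiver.
- Assumed: the correlation r between baseline HADS and ICG. The documents give none, so a range is shown.

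**The plan's own figure**

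Standard error of the difference: 11.7 × √(2/37) = 2.72. Normal approximation: 2.72 × (1.960 + 0.842) = 7.62. Noncentral t with 72 degrees of freedom: 7.72. The stated 7.7 reproduces.

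**With baseline HADS in the model**

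Residual SD = 11.7 × √(1 − r²), with one or two further degrees of freedom used; that choice does not alter the figures at two decimals. Noncentral t, 37 per group:

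| Assumed r | MDD | Reduction from 7.72 | Power at 7.7 |
|---|---|---|---|
| 0.2 | 7.57 | 2% | 0.81 |
| 0.3 | 7.37 | 5% | 0.83 |
| 0.5 | 6.69 | 13% | 0.90 |
| 0.6 | 6.18 | 20% | 0.94 |

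At r = 0.5 the variance falls by 25%, which is worth 37/(1 − 0.25) = 49 unadjusted caregivers per group.

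**How many would have a baseline score**

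60 deaths × 60% = 36 per group, against the projected 37. Most of the projected sample should therefore be enrolled caregivers. At 36 per group the unadjusted MDD is 7.83, and the adjusted values are 7.47, 6.79 and 6.27 at r = 0.3, 0.5 and 0.6.

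**Post-death HADS**

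The plan states no test and no MDD for it. Purely as illustration, borrowing the patient SDs from Table 4 (4.0 for anxiety, 3.9 for depression) and assuming r = 0.5, the MDD at 37 per group goes from 2.64 to 2.29 and from 2.57 to 2.23.

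**Is chance imbalance a further loss?**

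One standard error of imbalance in a standardised baseline score is √(2/37) = 0.23 SD. At r = 0.5 it moves the ICG difference by 0.5 × 11.7 × 0.23 = 1.36 points. Its square, 1.85, is 25% of 2.72² = 7.40. It is the same 25% that adjustment takes out of the variance, so it must not be counted again.

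**The case against.** The strongest reply is that the t-test is only a sizing device. A reader might infer that the plan commits itself to a raw two-group contrast, but the documents do not say so. The t-test appears only in C5.3, where the subgroup figure is described as applying before other covariate adjustment; the authors evidently size without covariates while expecting some. C5.2 speaks of mixed-effect methods, although that sentence follows the one on the QODD and its reach to ICG and HADS is unclear. This stands: what can be said is that no covariate is pre-specified, not that adjustment is ruled out.

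Second, the Aim 1 rule might already cover imbalance. A reader might therefore infer either that protection is complete or that it is absent; neither is supported. Aim 2 carries over the longitudinal methods of Aim 1 and then takes grief out of them, so the rule's reach is doubtful. Where it does apply, it waits for observed imbalance or for prediction of missingness or compliance. It would pass over a score that is balanced but prognostic, which is where the precision lies.

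Third, an unadjusted test is valid. Chance imbalance does not inflate its type I error and is already inside its standard error. This stands.

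Fourth, the gain rests on an assumed correlation. The intra-subject correlation of 0.5 in C5.3 is given for repeated measures while the patient is alive; it is not given for HADS against ICG, nor for HADS across bereavement. This also stands.

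Finally, the ICG-SF is listed among additional measures, not among the Aim 2 outcomes in Table 3, which limits how much weight the point can carry.

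**Conclusion.** The point holds as a minor one. The plan names no baseline covariate for ICG-SF or post-death HADS, although the obvious one is already collected from enrolled caregivers. The 7.7 is not an error; it is the correct unadjusted figure.

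The benefit runs from 5% or less off the MDD at r of 0.3 or below to about 20% at r = 0.6. It also brings control of measured baseline distress and a model fixed in advance.

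This rests on the assumed correlation and on the caregiver's baseline being taken before randomisation. C5.1 says so for patients, and the sequence in C3.1 implies it for caregivers.

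It is tempting to conclude that adjustment would make the two bereaved groups comparable. It would not. If the intervention changes who dies, a covariate for caregiver distress corrects only the measured part of the resulting difference; selection by survival remains. The plan itself projects equal deaths in the two groups.

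**What to change.** - In C5.2 (Specific Aim 2), pre-specify a linear model for ICG-SF and for post-death HADS with arm and the caregiver's baseline HADS: the matching subscale for post-death HADS, and both the anxiety and depression subscales for ICG-SF. Baseline burden is optional. Use the baseline score, not later pre-death scores, which the intervention may have altered. State whether the nesting sentence applies to these outcomes.
- Fit this model in enrolled caregivers who have a baseline score, about 36 per group.
- Add a sensitivity analysis of all respondents, including non-study caregivers, either unadjusted or with a missing-baseline indicator. The indicator should not carry the main analysis, because whether a study or non-study caregiver responds is settled after randomisation and may differ by arm.
- In C5.3, keep 7.7 as the unadjusted MDD. If wanted, add 7.4, 6.7 and 6.2 for r = 0.3, 0.5 and 0.6 at 37 per group, with the correlation labelled as an assumption.

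The cost is a few sentences, one or two degrees of freedom and one extra sensitivity analysis. No new data or participants are needed.
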